## Methods

### *Patient*

The present study was approved by the Ethics Committee of the VGHKS (No.VGHKS19-CT9-11). All patients were recruited from the VGHKS between October 2019 to January 2022. All patient provided informed consent before being enrolled in the study.

Inclusion criteria was: [1] Aged>20 [2] Scheduled to received operation that required general anesthesia with endotracheal tube [3] ASA I, II. Patient with fallow condition would be excluded: [1] Emergent surgery [2] pregnant [3] Limited mouth opening [4] Poor dental condition [5] Airway obstruction (oral tumor, hypopharyngeal cancer....etc) [6] Deep neck infection [7] Allergic to any anesthetic agent.

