### *Anesthesia protocol*

After the patient entered the operating room, monitor would be setup with electrocardiogram, non-invasive blood pressure, oxygen saturation, end-tidal carbon dioxide (PEtCO2). Intravenous access would then be established. Induction would be started right after setting the patient to sniff position and well pre-oxygenated. Endotracheal tube selection would fallow rules as below: Inner diameter 7.0mm for female patient, 7.5mm for male patient. As nasal endo, Inner diameter 6.5mm for female patient, 7.0mm for male patient. As Double lumen endotracheal tube 35 Fr for female patient, 37 Fr for male patient. Adjusted by patient's height as physician's clinical experience. Fentanyl 1-2 ug/kg, propofol 1.5-2mg/kg, rocuronium 0.6-1mg/kg or cisatracurium 1-2 mg/kg were administered intravenously as induction agent. Intubation was performed 3 minutes after muscle relaxant injection. Mechanical ventilation started right after the airway establishment.

During intubation, physician placed the tip of the video conventional Macintosh

blade at base of epiglottis to achieve glottic opening. Cormack-Lehane grade was then record as conventional attempt. Then physician placed the tip of the blade under the epiglottis and lift it to achieve glottic opening. Cormack-Lehane grade was record as Miller's attempt. Also, increased lifting force, BURP maneuver would be record if applied. If both attempts failed to intubate the patient, the process would switch to emergent difficult airway protocol and the patient would drop out the research. Three physicians attended this research had experience of anesthesia for 4, 6, 15 years with success intubation experience > 300+ cases.

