### *Statistics*

The patient data were presented as frequency and percentage for categorical variables or mean and standard deviation for continuous variables. The Cormack-Lehane grading during Miller versus Macintosh approaches was compared using the McNemar-Bowker test. The test was 2-tailed and  $P < 0.05$  was considered statistically significant. Data analyses were conducted using SPSS 26 (IBM SPSS Inc, Chicago, Illinois).

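### Does pooling three physicians' patients in one McNemar-Bowker test make the P value too optimistic?

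*Combined protocol and SAP*

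**What the plan says.** The Anesthesia protocol section describes the operators: "Three physicians attended this research had experience of anesthesia for 4, 6, 15 years", "with success intubation experience > 300+ cases". Each patient has two looks. The conventional one comes first ("Cormack-Lehane grade was then record as conventional attempt"), followed by the Miller-type one: "Then physician placed the tip of the blade under the epiglottis and lift it to achieve glottic opening". The text reads as one physician doing and grading both looks, and no separate grader is named. Manoeuvres that depend on the operator are noted: "increased lifting force, BURP maneuver would be record if applied".

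The Statistics section gives one comparison: "The Cormack-Lehane grading during Miller versus Macintosh approaches was compared using the McNemar-Bowker test", two-sided at 0.05. There is no operator stratum, operator term or table by physician. The text supplied gives no sample size and no split of patients among the physicians. It does not say that the operator is recorded for each case.

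**The concern.** McNemar-Bowker treats patients as independent pairs. Pairing removes whatever affects both looks equally, including a physician's overall skill. It does not remove a difference specific to one position, such as being better at lifting the epiglottis directly or grading that view more kindly. Such a difference moves all of that physician's pairs in the same direction.

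With three operators of 4, 6 and 15 years' experience, a pooled P below 0.05 could come mainly from one of them, most easily the one with the largest caseload, while another shows nothing or the reverse. Read as evidence about the technique in other hands, the P value would then be too small.

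**Working it through.** The plan states no sample size, power or operator variance, so it has no figure to reproduce. Only the three operators, the pooled test and the two-sided 0.05 level come from the documents. Everything else here is assumed: grades I to IV at 60/28/10/2%, latent within-patient correlation 0.7, operator-by-position effects drawn from N(0, τ²), and N = 100, 200 or 300. Unless stated otherwise, caseloads are equal and Bowker uses the non-empty cell pairs.

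**1. When is the pooled test sound?** With τ = 0 it rejects in 2.6–3.6% of null trials. A separate simulation let operators differ in overall skill only, with caseloads 70/20/10. It gave 3.2% at N = 100 and 3.7% at N = 200. Differences in general skill therefore do not inflate the test.

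**2. When does it over-reject?** The average effect is zero and operators vary by position:

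| τ (latent SD) | Caseload | Pooled Bowker, N = 100/200/300 |
|---|---|---|
| 0.1 | equal | between about 4% and 8% |
| 0.2 | equal | 7% / 14% / 21% |
| 0.2 | 60/25/15 | 8% / 19% / 27% |

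These rates count as errors only if the target is a wider population of operators. For the three physicians themselves, a non-zero caseload-weighted effect is a true effect.

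**3. Cross-check by design effect.** DE = 1 + (m − 1) × ICC, and actual alpha = 2 × [1 − Φ(1.96/√DE)].
- With m = 33 per operator and ICC 0.01, DE = 1 + 32 × 0.01 = 1.32 and alpha is 0.088.
- With ICC 0.05, DE = 1 + 32 × 0.05 = 2.60 and alpha is 0.224.
- The ICC of the grade difference implied by τ = 0.2 is 0.031. At N = 100, DE = 1 + (100/3 − 1) × 0.031 = 2.0, which gives alpha of about 0.17.

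The last figure matches a signed-rank test in the same simulation (17%). It does not match the planned Bowker test (about 7%), so design effects overstate the exposure of the test actually planned.

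**4. Does stratifying by operator cure it?** The comparator sums the Bowker statistics and degrees of freedom over the three physicians:

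| Setting, N = 100/200/300 | Pooled | Stratified |
|---|---|---|
| No average effect, τ = 0.2 | 7% / 14% / 21% | 8.5% / 20% / 35% |
| Common effect of 0.2 SD, τ = 0 (power) | 16% / 38% / 60% | 6% / 18% / 34% |

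Stratification still conditions on the same three people. It rejects more often when operators differ and less often when they share a real effect.

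**5. Should the overall effect be withheld when observed directions differ?** With an identical 0.2 SD effect in all three physicians, observed directions conflict by chance in about 31% / 16% / 10% of trials. A formal position-by-operator check has power of only 24% / 39% / 50% at τ = 0.2.

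**The case for a change.** The strongest case for a change is that the mechanism is plausible here. The view depends on blade handling, the operator apparently grades both looks knowing which is which, and lifting force and BURP are used at discretion. The plan does not limit its comparison to these three people, and without results by operator a reader cannot tell whether they agree. A different model, using binary pairs with 30% discordant, shows the same pattern. If one physician has 70% of 200 patients and is the only one with a real effect (75% of discordant pairs favouring Miller), the pooled test is significant in 79% of trials, against 24% if that physician has a third of them.

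The mechanism stands, and so does the value of seeing results by physician. The step from there to a faulty test does not. The absence of a stated limit is not a claim about all operators. The plan says who the operators were, and recruitment was at one hospital. The 79% figure is detection of a real effect in the physician who treated most of the patients. In about half of the significant signed-rank trials at τ = 0.2, at least one operator's true effect ran the other way. That largely reflects the set-up, since three independent effects centred on zero have mixed signs with probability 1 − 2 × (1/2)³ = 75% before any data. Random operator effects are no way out, because three clusters are too few to estimate their variance reliably.

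**Conclusion.** The concern does not call for a change. The planned test is valid for the hypothesis that none of these physicians differs between positions, and pairing cancels their overall skill. It becomes optimistic only when two conditions hold together: the result is carried over to other operators, and operators truly differ in their position effect. The documents make no such extension and give nothing from which to estimate that variance. The over-rejection of up to 21% with equal caseloads, or 27% with 60/25/15, rests on an assumed τ of 0.2 and an assumed N of 300. With τ = 0.1 and equal caseloads it is between about 4% and 8%.

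The analytic alternatives bring no gain. Stratification raises rejection under operator variation and roughly halves power at the two larger sample sizes. A rule keyed to observed direction would often suppress a real common effect. What remains is ordinary reporting: patient counts and paired grade shifts by physician if operator identity was recorded, and a conclusion worded for these three operators. Analysts can add that at the write-up, and it would leave the planned result unchanged.

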### *Statistics*

The patient data were presented as frequency and percentage for categorical variables or mean and standard deviation for continuous variables. The Cormack-Lehane grading during Miller versus Macintosh approaches was compared using the McNemar-Bowker test. The test was 2-tailed and  $P < 0.05$  was considered statistically significant. Data analyses were conducted using SPSS 26 (IBM SPSS Inc, Chicago, Illinois).

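### The only planned test, McNemar-Bowker, ignores the order of the Cormack-Lehane grades and has no direction, and no paired estimate or confidence interval accompanies it

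*Combined protocol and SAP*

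**What the plan says.** Under Anesthesia protocol, the same physician grades the same patient twice, in a fixed sequence. After the Macintosh position, "Cormack-Lehane grade was then record as conventional attempt"; after the blade tip is moved under the epiglottis, "Cormack-Lehane grade was record as Miller's attempt". The outcome is therefore a pair of ordered grades per patient. The number of grade levels is not stated.

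Under Statistics, "The Cormack-Lehane grading during Miller versus Macintosh approaches was compared using the McNemar-Bowker test". The section adds that "The test was 2-tailed", with significance at P < 0.05, and that "Data analyses were conducted using SPSS 26". The only other planned output is descriptive: "The patient data were presented as frequency and percentage for categorical variables", with means and standard deviations for continuous data.

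The text contains no ordered or directional test, paired effect estimate, confidence interval, sample size or power statement. It also does not say how Bowker's degrees of freedom are counted.

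**The concern.** Comparing two blade positions by grade of glottic view implies asking which view is better. McNemar-Bowker asks whether the cross-table of the two grades is symmetric, which is a different question.

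- **No direction.** Swapping Macintosh and Miller leaves the statistic and P value unchanged. Calling the test two-tailed does not give an omnibus chi-square a direction.
- **No order.** Relabelling the grades in any sequence leaves P unchanged, so a move from I to II counts the same as one from I to IV.
- **Diffuse.** With four grades there are 4 × 3 / 2 = 6 pairs. A consistent shift is spread over up to 6 df instead of being concentrated in one contrast.
- **Undefined df when grades are sparse.** If grades III and IV are rare, some pairs are empty. Counting 6 df or only non-empty pairs can then change the conclusion.

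A significant result would support only the statement that the table is asymmetric. A non-significant one could hide a consistent improvement. Neither comes with an estimate of size.

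**Working it through.** The plan states no figure to reproduce, so the check is of how the test behaves. All tables and distributions below are assumed for illustration.

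**Formula.** Bowker = sum over pairs i<j of `(n_ij - n_ji)^2 / (n_ij + n_ji)`. Arrows run from the Macintosh grade to the Miller grade; a higher grade is a worse view.

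**Worked tables**

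- *(a) As many improved as worsened, yet significant.* I→II 20, II→I 5, II→III 5, III→II 20. Improved 5 + 20 = 25; worsened 20 + 5 = 25. Bowker = 2 × (20 − 5)² / 25 = 18.0; P = 0.006 on 6 df. Sign test P = 1.0. The distributions do differ (I −15, II +30, III −15), so this is not a false positive, but P does not say which view is better.
- *(b) Identical distributions, yet significant.* I→II, II→III and III→I 12 each; reverse moves 3 each. Every grade loses 15 patients and gains 15. Bowker = 3 × (12 − 3)² / 15 = 16.2; P = 0.013 on 6 df, 0.001 on 3 df. Scored marginal homogeneity P = 1; signed-rank P = 0.71; McNemar on grade III-IV (15 entering, 15 leaving) P = 1.
- *(c) Most changes one way, yet not significant.* Improved:worsened over six pairs 9:3, 6:2, 3:1, 2:0, 1:0, 1:0, that is 22 versus 6. Bowker = 36/12 + 16/8 + 4/4 + 2 + 1 + 1 = 10.0; P = 0.12 on 6 df. Exact sign test on 22 of 28: P = 0.004. Signed-rank P = 0.002, taking the first three pairs as one-grade changes and the last three as I-III, II-IV and I-IV.
- *(d) The df convention decides.* All changes in one pair, 22 versus 6: Bowker = 16² / 28 = 9.14; P = 0.002 on 1 df, 0.17 on 6 df.

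**Cost of extra df.** A noncentrality of (1.960 + 0.842)² = 7.85 gives 80% power on 1 df. The same value gives 64% on 3 df, 52% on 6 df (four grades) and 43% on 10 df (five grades).

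**Simulated power.** Assumed: Macintosh 60/28/10/2%, Miller 70/22/7/1%; latent bivariate normal cut at these margins; two-sided 0.05; 20,000 tables per scenario (Monte Carlo SE at most 0.4 points).

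| Test | Correlation 0.7, N = 100/150/200 | Correlation 0.5, N = 100/150/200 |
|---|---|---|
| Bowker, 6 df | 16/36/55% | 12/26/41% |
| Bowker, non-empty pairs | 32/51/67% | 21/34/48% |
| Exact sign test | 53/73/86% | 40/57/71% |
| Signed-rank | 62/79/89% | 47/63/76% |

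Across these settings, 80% power needs about 260-380 patients with Bowker and about 160-220 with signed-rank. Type I error at N = 100-200 is 0.7-2.4% (Bowker, 6 df), 2.4-3.2% (Bowker, non-empty pairs) and 4.8-5.2% (signed-rank), so the gain does not come from an inflated error rate.

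**A second set of assumptions.** With grades at 50/30/15/5%, correlation 0.5, a constant shift of 0.3 SD and N = 100, Bowker on non-empty pairs has 31% power and scored marginal homogeneity 65%.

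**Where the gap narrows.** At N = 400 under the tabulated margins it is 94-95% versus 99.5% (correlation 0.7) and 83-84% versus 97% (0.5). With a larger shift (Miller 80/16/3/1%, N = 100, correlation 0.7) it is 89-96% versus 99.5%. It is nil when all changes fall in one pair and df counts only that pair.

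**The case against.** McNemar-Bowker is a legitimate test for paired categories. It respects the pairing and was conservative in the simulations, so the plan does not create excess false positives. The supplied text states no objective, so the question of which view is better is inferred. The planned frequencies would show direction informally, and any two-sided P value reported without its statistic or estimate lacks direction too. All of this is right. It makes the choice a mismatch, not an error. Marginal percentages, however, need not show how many patients improved or worsened, and they carry no measure of uncertainty.

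The power figures rest wholly on assumptions, and grades III-IV may be rare in these elective ASA I-II patients with airway obstruction excluded. With 85/14/0.9/0.1% versus 92/7.5/0.4/0.1% (also assumed) and correlation 0.7, Bowker on non-empty pairs has about 39% power at N = 100 and 69% at N = 200, close to the sign test's 41% and 75%. That narrows the gap but does not close it: signed-rank gives 49% and 81%. On 6 df, Bowker falls to 3% and 26%, which makes the unstated convention more important.

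Two limits stand. In table (a), signed-rank gives P = 1.0 and misses a real change in spread that Bowker detects, which is a reason to keep Bowker. And no ordered test removes an effect of always grading Macintosh first.

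**Conclusion.** The concern holds. The sole planned test uses neither the order of the grades nor the direction of change, and nothing planned estimates the paired difference with its uncertainty. These points follow from the formula and the text and need no assumed data.

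The size of the power loss cannot be fixed from the documents, because sample size, grade levels and grade distribution are absent. Under the tabulated assumptions, at N = 100-200, Bowker trails signed-rank by roughly 20 to 46 points (for example 67% versus 89%, and 16% versus 62%). The gap is smaller with large samples, larger shifts or rare high grades under the non-empty-pairs convention. This should be corrected, but it does not invalidate the comparison; confidence in its practical importance is medium.

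**What to change.** Make one ordered paired test the main comparison: Wilcoxon signed-rank on the paired grades, two-sided at 0.05, with the exact sign test as a sensitivity analysis. Marginal homogeneity with ordered scores would also serve. Report percent improved minus percent worsened with a 95% CI and, as secondary, the paired difference in the proportion with grade III-IV with a 95% CI. Keep McNemar-Bowker as supportive and state its df convention.

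The Patient section says that "All patients were recruited from the VGHKS between October 2019 to January 2022", so the data may already have been seen. If so, report the Bowker result as well and label the ordered test and the estimates as post hoc; they then carry less weight.

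The cost is a few lines of text on the same data. Signed-rank and scored tests must rank or score the grade changes; the sign test avoids this with somewhat less power.
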